below the anticipated MTD of CX-2009 and therefore inconsistent with the recommendations of [Saber 2015](#). Additionally, the GLP toxicity study findings for CX-2009 are similar to those reported for other maytansinoid ADCs and are consistent with the effects of DM4.

Another approach to FIH starting dose selection for anticancer ADCs is to use 1/6 of the highest nonseverely toxic dose (HNSTD) in cynomolgus monkeys, scaled for body surface area (BSA). This formula has generally been found to result in an acceptable balance of safety and efficient dose escalation in Phase 1 trials of ADCs ([Saber 2015](#)). An HNSTD was not defined in the GLP toxicity study of CX-2009 due to histopathological findings of axonal degeneration, which did not reverse over a 3-week dose-free interval. There were no clinical observations consistent with functional neuropathy.

Peripheral neuropathy is a well-described side effect of MTIs ([Dumontet 2010](#)). While generally not dose limiting, peripheral neuropathy has been reported in clinical trials of Kadcyla as well as most DM4-ADCs and is an expected toxicity for CX-2009 ([Diéras 2014](#), [Moore 2017](#)).

Resolution rates of ADC-related peripheral neuropathy have ranged from ~19.0% to 54.0% upon treatment discontinuation ([Stagg 2016](#)).

In [Table 3](#), CX-2009 is compared to 2 other maytansinoid ADCs, IMGN242 and Kadcyla, which also produced axonal degeneration in monkeys. The dose-dependent incidence and low severity of axonal injury associated with CX-2009 in monkeys appears generally similar to that of Kadcyla and IMGN242, which have been safely administered to cancer patients at starting doses of 0.3 mg/kg and 0.5 mg/kg, respectively.

Table 3. Neurotoxicity of CX-2009 and Other Maytansinoid ADCs in Monkeys

Article (Schedule)	GLP Toxicity Study (Cynomolgus)			Clinical Starting Dose (mg/kg) MTD (mg/kg) DLT
	Dose Levels (mg/kg)	Axonal Degeneration, Sciatic Nerve: Incidence, Severity ^a	Axonal Degeneration, Spinal Cord: Incidence, Severity	
CX-2009 (q3w×2)	5 10	4/12, minimal to mild 8/12, minimal to mild	5/12, minimal 11/12, minimal	
C16-026	15	10/10, minimal to mild	10/10, minimal	
IMGN242 (huC242-DM4) (single dose)	5 (NOAEL) 15 (HNSTD)	0/2 2/2, Grade 2	0/2 2/2, Grade 1	5 4.54 Blurred vision (Goff 2009)
CRT18-001	25	NE ^b	NE	
Kadcyla (T-DM1) (q3w×4) (Poon 2013)	3 10 (HNSTD) 30	0/14 6/14, minimal 14/14, slight to severe	0/14 8/14, minimal 14/14, slight to severe	0.3 3.6 Thrombocytopenia (Krop 2010)

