10.1 General Statistical Methodology

Data will be analyzed using SAS (Version 9.4 or higher). All consented subjects are identified by an 8-digit Subject Number where the first four digits represent site and the last four digits are the sequential enrollment within a site (e.g. 1234-0001).

Descriptive statistics will be tabulated as follows:

- Categorical data will be summarized in contingency tables presenting frequencies and percentages.
- Continuous data will be summarized using number of non-missing values (n), mean, median, standard deviation, and median and range values. Where relevant, Q1 and Q3 may be presented.

The tables will be created by dose level and by cancer type, unless otherwise specified. For tables by dose level, all available data from Parts A, A2, and B will be pooled with ≤ 2 mg/kg presented as a single dose group and 4, 5, 6, 7, 8, 9, 10 mg/kg presented as separate dose groups; Part C1 dosing 4 mg/kg Q2W and 6

mg/kg Q2W will also be presented as separate dose groups. Data from planned, protocol-specified visits and unplanned visits will be included in listings, unless otherwise noted. Baseline tables will contain a total column when appropriate.

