10.1.1 Handling of Missing Data

All data will be analyzed as they were collected in the database. Missing data, other than as described in Section 0, will not be imputed.

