10.1.2 Derived and Computed Variables

The following derived and computed variables have been initially identified as important for pre-specified and exploratory analyses. Additional computed variables may be required to aid in analysis.

Missing Date Components of AEs, Concomitant Medications (including Prior Cancer Treatments), and Medical History

Every attempt will be made to obtain complete dates for any AEs, CMs, and Medical History; however, in the case of incomplete dates, the missing Day, Month or Year will be represented in listings as "UN", "UNK" or "UNKN", respectively. Missing Hour or Minute in times will be represented as "UN".

Missing date components for AEs, CMs, and Medical History will not be imputed; however, AEs with incomplete start dates (and times, in the case of infusion-related reactions) will be attributed to treatment according to the following algorithm:

- Only the year is reported: If the year is after or the same as the day of the first dose, the event will be considered treatment-emergent.
- Only the month and year are reported: If the month is after or the same as the day of the first dose, event will be considered treatment-emergent.
- Only the time is missing: If the event occurred on or after the day of the first dose in the treatment period, then the event will be considered treatment-emergent.

Dates with missing day values will be imputed to the 15th of the month when calculating time since the last prior cancer regimen or procedure. If a date is missing both day and month values, then the date will not be imputed and the prior cancer regimen or procedure will not be considered for selection as the last.

Study Days Relative to First Infusion of Study Medication

Study Day 1 is the day of the first infusion of CX-2009 (for subjects enrolled only to the main CTMX-M-2009-001 study) or the day of the first treatment with Zr-CX-2009 (for subjects enrolled to the CTMX-M-2009-001 imaging substudy); negative Study Days occur prior to first infusion of study treatment; and positive Study Days are those after the first study treatment – e.g., Study Day -1 is the day immediately preceding the first study treatment, Study Day 2 is the day immediately following the first study treatment.

Time on Study

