Time on study (months) is calculated as the study termination date minus the first infusion date (+1) – this value is divided by 30.4375 to obtain the time in months. If the study termination date is missing, the data cutoff date will be used.

Time Since Prior Regimens or Procedures

Time since prior regimens or procedures (weeks) is calculated as the first infusion date minus the end date of the last prior (relative to study) regimen or procedure (+1) – this value is divided by 7 to obtain the time in weeks. Regimen or procedure end dates will be imputed to the 15th of the month when only the month and year are reported. If only the year is reported, then end date will not be imputed and the regimen or procedure will not be eligible for selection as the last prior regimen or procedure.

Time Since Initial Histopathological Diagnosis

Time since initial histopathological diagnosis (years) is calculated as the date of informed consent minus the date of the initial histopathological diagnosis (+1) – this value is divided by 365.25 to obtain the time in years.

Time Since Most Recent Disease Recurrence/Progression

Time since most recent disease recurrence/progression (years) is calculated as the date of informed consent minus the date of the most recent disease recurrence/progression (+1) – this value is divided by 365.25 to obtain the time in years.

AEs with Missing Relationship

Every attempt will be made to obtain complete information for AEs regarding relationship(s); however, in the case of missing data:

- AEs with missing relationship designations will be considered “Related” to study treatment provided the AE onset date/time occurs on or after the initial dose of CX-2009 was initiated.

Duration of Treatment

Duration of treatment for CX-2009 will be derived by subtracting the start date of the first infusion from the stop date of the last infusion (+1) - this value is divided by 30.4375 to obtain the time in months.

Percent of Infusion

The percent of each dose received will be calculated using the following formula rounded to one decimal place:

$$\text{Percent of Dose} = \frac{\text{Total Dose of Study Medication Administered} \times 100}{\text{Total Planned Dose of Study Medication}}$$

Duration of Infusion (min)

Duration of infusion in minutes will be derived by subtracting the Infusion Start Time from the Infusion Stop Time.

Laboratory Values with < or > Inequality Symbols

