- TEAEs leading to death related to CX-2009
- TEAEs of Special Interest by maximum severity grade
- TEAEs of Ocular Toxicity related to CX-2009 by maximum severity grade
- TEAEs of Neuropathy related to CX-2009 by maximum severity grade
- TEAEs of Hepatic Disorders related to CX-2009 by maximum severity grade
- TESAEs
- Grade 3 or higher TESAEs
- Grade 3 or higher TESAEs related to CX-2009

Each subject will be counted only once within each level of the summary (PT or SOC). If a subject experiences more than one TEAE within a PT or SOC, only the TEAE with the strongest relationship or the maximum severity, as appropriate, will be included in the summaries of relationship and severity.

The above list of summary tables will also be produced by MedDRA PT (based on descending frequency of the total column) by dose level or by cancer type.

The TEAE summary tables by SOC and PT will be provided upon request to the DSMB.

TEAE profile summaries will also be created for infusion reactions. This table will summarize the frequency of events, time from event onset to the start time of the first infusion (hours), time from the event onset to the start time of the most recent infusion (hours), duration of the event (hours), duration category (<1 hour, 1 to 6 hours, >6 hours), severity grade, outcome, action taken, and other action taken with medication.

Profile summaries will also be created for TEAEs of Ocular Toxicity, TEAEs of Neuropathy, and TEAEs of Hepatic Disorders. These tables will summarize the time from event onset to the start time of the first infusion (days), duration of the event (days), duration category (<=7 days, 7 to 14 days, >14 days), severity grade, outcome, action taken, and other action taken with medication.

A tabular summary of deaths by study period (Screening, Treatment, Follow-Up) will be provided by dose level and by cancer type.

No inferential statistical tests will be performed for safety analyses.

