Estimates of time-to-event endpoints (DOR, TTR, PFS, and OS) will be obtained using the Kaplan-Meier method. Kaplan-Meier curves will be provided for these endpoints. A swim lane plot will be provided for DOR. DOR and TTR will also be summarized using descriptive statistics for confirmed objective responders.

The median, and 95% CIs around the DOR, TTR, PFS, and OS will also be calculated using the Kaplan-Meier method. The range of TTR, PFS and OS will be provided as well. Frequencies and percentages will be summarized for event rates and censored observations of the time-to-event endpoints. Six- and twelve-month and 2-year survival rates will be included as well. The number and percentage of disease progressions and deaths will be included (replacing the event rate) in the PFS summary.

CBR16 and CBR24

Breast cancer patients will also have CBR16 and CBR24 summarized by dose level and also by cancer subtype (TNBC, HR+/HER2-, HER2+). CBR16 is defined as the proportion of subjects with best overall response of CR or PR or with SD for at least 16 weeks. CBR24 is defined as the proportion of subjects with best overall response of CR or PR or with SD for at least 24 weeks. CBR16 and CBR24 will only be calculated for subjects in the REP.

SD Duration is defined as the time interval from the start of the treatment to the date of subsequent PD or on-treatment death. In the absence of PD or on-treatment death before the analysis cut-off date, it is the time from the start of treatment to the date of the last adequate tumor assessment before the cut-off date.

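### SAP 12.1 summarises the duration of ocular, neuropathy and hepatic events with no rule for events still ongoing, so by default the duration rows reflect resolved events only and are biased downward

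*SAP*

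**What the plan says.** SAP 12.1 plans profile summaries for three groups of treatment-emergent events: ocular toxicity, neuropathy and hepatic disorders. On their content it says: "These tables will summarize the time from event onset to the start time of the first infusion (days), duration of the event (days". The same sentence goes on to the categories and the outcome: "duration of the event (days), duration category (<=7 days, 7 to 14 days, >14 days), severity grade, outcome, action taken". No formula for duration is given there or among the derived variables in SAP 10.1.2.

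The general rules that would then apply are:

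- SAP 10.1: "Continuous data will be summarized using number of non-missing values (n), mean, median, standard deviation, and median and range values".
- SAP 10.1.1: "Missing data, other than as described in Section 0, will not be imputed". The reference to Section 0 is broken and appears to mean 10.1.2.
- SAP 10.1.2: "Missing date components for AEs, CMs, and Medical History will not be imputed". The only algorithm for adverse event dates in that section concerns incomplete start dates.
- SAP 13.1.2: Kaplan-Meier estimation is assigned to DOR, TTR, PFS and OS. Adverse event duration is not among them.

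Elsewhere the SAP does close open-ended intervals. For time on study: "If the study termination date is missing, the data cutoff date will be used". For the duration of stable disease without progression or on-treatment death: "it is the time from the start of treatment to the date of the last adequate tumor assessment before the cut-off date".

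The protocol expects some events not to resolve. Section 8.4 lets follow-up of an adverse event stop at stabilisation or at a new therapy. Table 9 in Section 5.5.4.1 lets weekly ocular assessments stop once the investigator judges the symptoms irreversible. Section 1.3.3 states: "Resolution rates of ADC-related peripheral neuropathy have ranged from ~19.0% to 54.0% upon treatment discontinuation".

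**The concern.** An event still open at last contact or at the data cut has no end date. If duration is computed only where an end date exists, open events leave both the continuous summary and the categories. Whether an event is open depends on how long it lasts, so this loss is not random: longer events are more likely to be missing, and what remains is too short on average.

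At stake is how persistent ocular and nerve toxicity appears in the report. At the November 2019 data lock, 42 of 92 subjects had related ocular toxicity and 26 of 92 had related peripheral neuropathy (Protocol 1.3.4.1), so these tables will not be empty. SAP Section 1 says its analyses will support safety committee review, publications and regulatory submissions. The cut-points of 7 and 14 days are also time limits that the protocol itself uses (Table 5 in Section 3.3; Tables 8 and 9 in Section 5.5.4.1), and the first two categories overlap at exactly 7 days.

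**Working it through.** **The plan's own figure.** The documents state no event duration and no precision for one, so there is nothing to reproduce. The background counts check: 26/92 = 28.3% and 42/92 = 45.7%, as stated.

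**Step 1: what the rules produce.** An ongoing event has no end date. SAP 10.1.1 supplies none, SAP 10.1.2 has no algorithm for one, and SAP 10.1 summarises only non-missing values. SAP 13.1.2 does not extend censoring to this variable. The event therefore has no duration and no category.

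**Step 2: direction and possible size (illustration).** Assume exponential time to resolution, and let q be the share of events resolved when observation ends.

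- Fixed follow-up: mean among resolved / true mean = 1 − (1 − q)·(−ln(1 − q))/q. The ratio of medians is −ln(1 − q/2)/ln 2.
- Exponential censoring: mean among resolved / true mean = q.

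For q = 0.54 with fixed follow-up: −ln(0.46) = 0.777, and 1 − 0.777 × 0.46/0.54 = 0.34.

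| q | Fixed: mean ratio | Fixed: median ratio | Exponential censoring: mean ratio |
|---|---|---|---|
| 0.19 | 0.10 | 0.14 | 0.19 |
| 0.54 | 0.34 | 0.45 | 0.54 |
| 0.80 | 0.60 | 0.74 | 0.80 |
| 0.90 | 0.74 | 0.86 | 0.90 |

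The values 0.19 and 0.54 are the ends of the neuropathy range in Protocol 1.3.3. The values 0.80 and 0.90 are assumed, for events that mostly resolve. Every ratio is below 1.

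**Step 3: categories.** Assume a true mean of 60 days and exponential censoring. The true share lasting over 14 days is exp(−14/60) = 79%. Among resolved events it is exp(−14/(60q)): 29% at q = 0.19, 65% at q = 0.54 and 75% at q = 0.80.

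**Step 4: counts.** If the cited range applied to the 26 subjects with neuropathy, at one event each (both assumptions), 26 × 0.19 = 4.9 to 26 × 0.54 = 14.0 would have an end date. About 12 to 21 would have none.

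**Step 5: would the cutoff date do as an end date?** It keeps the events in the table, but with fixed follow-up the mean recorded duration is q times the true mean. That is still too short, so filling in the missing date is not enough.

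**Step 6: does censoring repair it?** In a simulation of 400,000 events with a true mean of 60 days, the censored-data estimate (total observed time divided by number resolved) was 59.9 to 60.1 days at q = 0.19, 0.54 and 0.80. The means among resolved events were 11.3, 32.4 and 48.0 days.

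**The case against.** The SAP nowhere says that it will exclude unresolved events. It gives no formula, so the exclusion is inferred from defaults. Its rule on date components concerns partly recorded dates, and an absent end date is not quite that. A programmer could also place an event already observed for more than 14 days in the top category without imputing anything. This stands as far as it goes: the defect is an unspecified rule, not a declared exclusion. But the non-missing-values and no-imputation rules still lead to exclusion by default, and no passage points elsewhere.

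The shortfall would also be visible. The same tables give outcome, grade and action taken for all events, the number of non-missing durations is reported, and the listings carry start and end dates. So it would be wrong to say that the tables as a whole describe only resolved events. Visibility does not correct the duration rows, though, and nothing links outcome to duration.

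The data may be more complete than feared. Protocol 8.4 asks that related events be followed to resolution or a stable state, and the final analysis follows database lock. The share still open at that point is unknown.

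Finally, Kaplan-Meier by dose level would be thin: 9 subjects had received 7 mg/kg at the data lock (Protocol 1.3.4.1), and 3 were enrolled in Part B (SAP 4.2). Stopping follow-up at death or new therapy may be informative, and a subject can have several events. These are fair limits. They argue for pooling dose levels and reading the median descriptively, and they do not favour a summary of resolved events alone.

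**Conclusion.** The concern holds for the duration and duration-category rows of three descriptive tables. Applied as written, the SAP leaves ongoing events out of those rows and biases them downward. The direction is firm because longer events are more likely to be unresolved. The size cannot be derived from the documents: the ratios above rest on an exponential model and assumed shares resolved.

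A reader might infer more, and the documents do not support it:

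- **That 46% to 81% of events would be lost.** The 19% to 54% range concerns neuropathy with ADCs after treatment discontinuation, with no time horizon and no CX-2009 data. It shows that unresolved neuropathy is to be expected. It does not carry over to ocular or hepatic events.
- **That the worst events are the ones missing.** Persistence is not severity. Of the 26 subjects with neuropathy, 13 had Grade 1 events and 5 had Grade 3. An event that began just before the cutoff is open without being long.
- **That the choice of 7 mg/kg is undermined.** That choice was made in November 2019 on the frequency of Grade 3 or higher ocular toxicity, clinical activity and PK simulation (Protocol 5.2.1.2), not on event duration.

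Incidence, grade, DLT and ORR results are untouched, and no inferential safety tests are planned. The point should still be corrected, because the default gives a biased summary and the remedy needs no new data. The overlap at day 7 is a minor matter to correct at the same time.

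**What to change.** In SAP 12.1, for the ocular, neuropathy and hepatic profile tables:

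1. Define duration as end date minus start date + 1.
2. Report n (%) of events resolved and ongoing.
3. Treat unresolved events as right-censored at the last adverse event assessment, death or data cutoff. Report the Kaplan-Meier median time to resolution, pooled across dose levels where events per dose are few.
4. Use categories of ≤7, 8–14 and >14 days. Put an ongoing event already observed for more than 14 days in the last category, and show shorter ongoing events in a separate ongoing row.

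The cost is a few lines of SAP text and three re-programmed tables, using dates already collected. Reported durations will become longer.

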12.2 Study Drug Administration and Exposure

Drug exposure will be summarized by CX-2009 Monotherapy dose level and by cancer type. The number of doses administered for CX-2009 will be summarized categorically and continuously. The duration of treatment (in weeks) will be summarized continuously as will the percent of dose of each study drug.

The duration (weeks) will be calculated as (date of last dose of study drug - date of first dose of study drug + 1)/7.

The number and percent of subjects who were administered a dose different from the planned total dose and the reason they received a dose different from the planned total dose will be summarized. Subjects may have more than one reason in this summary.

A listing of exposure to the study drugs will be provided.

12.3 Concomitant Medications

All medications taken within 30 days before the administration of study drug and all concomitant medications and therapies administered during the study will be recorded on the relevant eCRF. Prior medications are defined as medications taken before the date of the first infusion. Concomitant medications are defined as medications taken on or after the baseline visit during the study treatment period. If a medication is taken on the date of the first infusion and is continued after the Baseline visit, it will be considered as both a prior and concomitant medication. Medications will be coded using the World Health Organization Drug Dictionary (WHODrug) version dated March 2020 (B3). Concomitant medications will be tabulated. Medication data will be summarized by Anatomic Therapeutic Classification (ATC) Level 4 within ATC Level 2 by dose level and by cancer type. Each subject will only be counted once within each level of the summary (ATC level 2 or ATC level 4).

12.4 Clinical Laboratory Tests

The clinical laboratory tests collected on study are as follows:

- Hematology: Red Blood Cells, Hemoglobin, Hematocrit, Platelet, White Blood Cells, Absolute Neutrophils, Neutrophils, Absolute Lymphocyte, Lymphocyte, Absolute Monocyte, Monocyte, Absolute Basophils, Basophils, Absolute Eosinophils, Eosinophils, Blast Count, Reticulocyte count, MCV, MCH, MCHC
- Blood chemistry: Albumin, Total Protein, Uric Acid, Sodium, Potassium, Chloride, Calcium, Calculated Creatinine Clearance, Phosphorus, Chloride, Bicarbonate, CO₂, Blood Urea Nitrogen (BUN), Hemoglobin A1c, Urea, Creatinine, Lipase, Amylase, Magnesium, Glucose, Lactate Dehydrogenase (LDH), Serum ALT, Serum AST, Total Bilirubin, Alkaline Phosphatase.
- Coagulation: Prothrombin time (PT) (sec), activated Partial Thromboplastin Time (aPTT) (sec), International Normalized Ratio (INR)
- Urinalysis:
 - Blood, Protein, Glucose as negative, trace, positive, 0, +, ++, +++, >+++ (listings only)
 - Specific gravity, pH, Leukocytes, Ketones, Urobilinogen: Low, normal, high

Select laboratory tests will be graded using the NCI-CTCAE version 4.03. The lab tests will be assigned Grades 1, 2, 3, or 4 if they meet the CTCAE criteria, regardless of designation of "Low" or "High" for the value. Grading will only be performed based on quantitative criteria (e.g. no clinical input required for grading). The following toxicities will be graded: aPTT prolonged, ALT increased, Hypoalbuminemia, ALP increased, AST increased, Blood bilirubin increased, Hypocalcemia, Hypercalcemia, Creatinine increased, Hypoglycemia, Hyperglycemia (fasting), Anemia, Hemoglobin increased, INR increased, Lymphocyte count decreased, Lymphocyte count increased, Hypomagnesemia, Hypermagnesemia, Neutrophil count decreased, Hypophosphatemia, Platelet count decreased, Hypokalemia, Hyperkalemia, Hyponatremia, Hyponatremia, White blood cell count decreased, Leukocytosis.

Shift tables will be created separately for Hematology and Blood Chemistry parameters, by dose level and by cancer type. The presentation in the table will be by CTCAE toxicity, and Grade 0 will be assigned for those values which are available and not assigned Grade 1, 2, 3 or 4. If the toxicity is bi-directional (e.g. Lymphocyte Count decreased, Lymphocyte count increased), then for the high direction Grade 0 will be assigned for the "low" direction. Similarly, for the low direction, Grade 0 will be assigned for the "high" direction. The shift tables will present shifts from baseline to worst post-baseline value. The worst post-baseline value could be any non-missing value collected after the first infusion up to and including 30 days after the last infusion.

Listings that include all laboratory results for any subject with any laboratory result outside of the normal range will be provided.

